4.9. Data analysis

• The detailed methodology for data analysis is explained in the SAP.

• For each age category, apixaban and warfarin cohorts whose patient characteristics are balanced by propensity score matching or IPTW methods will be created, and incidence rates of stroke/SE or major bleeding in each cohort and hazard ratios+ 95% confident intervals will be calculated.

4.10. Milestones

Data extraction from MDV database: Jun 30 – Jun 30, 2022 Analysis: July.01 - Aug.31, 2023 Completion of final study report: Sep.8, 2023 Manuscript submission: Oct.31, 2023

•

5. AMENDMENTS AND UPDATES

| Amendment number | Date | Protocol section(s) changed | Summary of amendment(s) | Reason |
|---------------------|------|-----------------------------------|-------------------------|--------|
|---------------------|------|-----------------------------------|-------------------------|--------|

| 1.1 | 22 JUNE, 2022 | 4.10 6 | Change the date; extraction from MDV database, start and end of data collection | The scheduled Data extraction date has changed. |
|-----|---------------------|--------------------------|---|---|
| 2.0 | 10 AUG, 2023 | 4.5 4.10 6 9.10 | Change the patient registration period Change the date of Milestones Change the data analyst | The launch date of apixaban in Japan was considered for concurrent comparison with warfarin. And the scheduled date FSR has changed. |

6. MILESTONES

| Milestone | Planned date |
|--|--------------|
| <completion assessment="" feasibility="" of=""></completion> | 28 Apr 2022 |
| Start of data collection | 30 Jun 2022 |
| End of data collection | 30 Jun 2022 |
| Final study report | 8 Sep 2023 |

7. RATIONALE AND BACKGROUND

Japan is a very elderly society compared to other countries in Europe and the United States, and there are many very elderly patients wth NVAF who are treated with any of anticoagulant and there are considerable number of patients who are newly diagnosed with NVAF even in their 80's and 90's. Most of these very elderly people have many complications, including severe ones, and take many medications chronically.In addition, many elderly patients have low body weight, sarcopenia, low ADL, frailty or frail-like characteristics, or high risk of falls. There has been much debate and inconclusive evidence on the value of anticoagulation for these very elderly patients with NVAF.

ARISTOTLE study has shown that apixaban is superior or equivalent to warfarin in various populations including populations at higher risk. However, there are few studies in the real-world settings regarding very elderly patients who are at higher risk.

9. RESEARCH METHODS

9.1. Study design

This is a retrospective non-intervention observational study to evaluate the difference in safety and effectiveness between apixaban and warfarin using a database provided by Medical Data Vision Co. Ltd. (MDV Co. Ltd.). Eligible patients will be extracted from the database and allocated to the pre-defined cohorts based on the actual age, age of NVAF diagnosis and types of anticoagulant therapy.

Based on the age category and anticoagulants on the index date (a date when patients initiated an anticoagulant for prevention of stroke/SE), eligible patients will be allocated to some cohorts. Patient characteristics will be balanced by an Inverse probability of treatment weighting (IPTW) method, and risk of stroke/SE (primary effectiveness endpoint) and major bleeding (primary safety endpoint) will be compared. Hazard ratios and 95% confident intervals will be calculated by using a COX proportional hazard method.

The following definitions will be used here

• Index date: the date when warfarin or apixaban was initiated

• Baseline period: the 180 days before the index date

• Cohorts:

- > Apixaban cohorts: patients who started an anticoagulant therapy with apixaban
- > Warfarin cohorts: patients who started an anticoagulant therapy with warfarin

• Observational period:

Follow-up period starts from the next day of the index date and ends depending on following outcomes which observed first.

- 1. Major bleeding when the target outcome for the analysis is major bleeding.
- 2. Composite of (ischemic or hemorrhagic) stroke and SE when the target outcome for the analysis is the composite endpoint.
- 3. Any bleeding when the target outcome for the analysis is any bleeding.
- 4. Discontinuation of the index OAC: The index treatment will be "discontinued" if the index OAC is not prescribed within 45 days after prescription refill date (calculated from the last refill date plus days of supply) of the index OAC, even though the patient has >1 medical encounter records after more than 45 days following the prescription refill date. The supposed prescription refill date is regarded as the last day of the follow-up for discontinued patients.
- 5. Switching from the index OAC: The index treatment is regarded as "switched" if non-index OAC is prescribed within 45 days after prescription refill date of the index OAC when the patient has 1> medical encounter records after more than 45 days following the prescription refill date. The switched day is regarded as the last day of the follow-up for the switched patients.
- 6. Withdrawal from the database: The patients are regarded as "withdrawal" from the database if the index OAC is not prescribed within 45 days after prescription refill date of the index OAC and there is no data of the patient on the database after prescription refill date. The last medical encounter is regard as the last day of the follow-up for patients withdrawn from the database.

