9.3.1. Inclusion criteria

Patients must meet all the following inclusion criteria to be eligible for inclusion in the study.

- 1. Diagnosed with AF anytime in the baseline period or on the index date, also have definitive diagnosis of AF anytime in the baseline period, on the index date, or post-index period.
- 2. Prescribed apixaban or warfarin on or after the day of AF diagnosis. The first observed prescription will be used to identify the patient's index date and treatment cohort
- 3. No use of the any OACs during the baseline period (the 180 days before the index date)
- 4. Age of 18 years or older on the index date.
- 5. Index date is at age 80 or older

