4. ANALYSIS SETS/POPULATIONS

4.1. FULL ANALYSIS SET

4.1.1. Inclusion criteria

Patients must meet all the following inclusion criteria to be eligible for inclusion in the study.

1. Diagnosed with AF anytime in the baseline period or on the index date, also have definitive diagnosis of AF anytime in the baseline period, on the index date, or post-index period.

PFIZER CONFIDENTIAL

Page 7 of 51

- 2. Prescribed apixaban or warfarin on or after the day of AF diagnosis. The first observed prescription will be used to identify the patient's index date and treatment cohort
- 3. No use of the any OACs during the baseline period (the 180 days before the index date)
- 4. Age of 18 years or older on the index date.
- 5. Index date is at age 80 or older

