4.1.2. Exclusion criteria

Patients meeting any of the following criteria will not be included in the study:

- 1. Having a diagnosis of valvular atrial fibrillation, post-operative atrial fibrillation, rheumatic atrial fibrillation or mechanical-valvular atrial fibrillation during the baseline and post-index period
- 2. Having a cardiac surgery procedure record during the baseline period
- 3. Having a joint replacement procedure record during the baseline period
- 4. Having a procedure of prosthetic heart valve during the baseline period
- 5. Having a diagnosis of venous thromboembolism during the baseline period
- 6. Female patients with pregnancy during the follow-up period
- 7. Patients prescribed "off-label" doses of OACs (per Japanese package insert of each OAC) or patients treated with OAC but in "off-label" or "contraindicated" manners.

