7.1.2.1. Calculation of propensity score

Propensity scores will be estimated by calendar year of index date based on multivariable logistic regression analyses that incorporate potential predictors of therapy as independent variables in the regression and cohort status (prescription of warfarin or apixaban) as the outcome. Consecutive calendar years of index dates may be collapsed to build logistic regression model with robustness. The following covariates will be included in the logistic regression:

- age on index date
- age at NVAF diagnosis
- gender

PFIZER CONFIDENTIAL

- CHADS₂ score in baseline
- CHA₂DS₂-VASc score in baseline
- heart failure diagnosis in baseline
- coronary heart disease diagnosis in baseline
- peripheral arterial disorder diagnosis in baseline
- myocardial infarction diagnosis in baseline
- hyperthyroidism or thyrotoxicosis in baseline
- TIA diagnosis in baseline
- stroke or SE diagnosis in baseline
- renal dysfunction diagnosis in baseline
- liver dysfunction diagnosis in baseline
- bleeding diagnosis in baseline
- hypertension diagnosis in baseline
- diabetes mellitus diagnosis in baseline
- treated with antiplatelet drug in baseline
- treated with NSAIDs in baseline
- treated with gastric secretion inhibitor in baseline
- treated with statin-based drug in baseline
- treated with anti-hypertensives in baseline
- treated with anti-arrhythmics in baseline
- treated with beta-blockers in baseline
- treated with heparins in baseline
- cardioversion in baseline

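### The index date falls in neither the baseline period nor follow-up, so exclusions 2-5 and the propensity model's diagnosis, score and procedure terms miss records dated that day

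*Protocol*

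**What the plan says.** Protocol 9.1 gives three definitions:

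- "Index date: the date when warfarin or apixaban was initiated"
- "Baseline period: the 180 days before the index date"
- "Follow-up period starts from the next day of the index date"

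The eligibility rules are the same in Protocol 9.3 and SAP 4.1. Inclusion 1 asks for a patient "Diagnosed with AF anytime in the baseline period or on the index date", together with a "definitive diagnosis of AF anytime in the baseline period, on the index date, or post-index period". Inclusion 3 is the washout: "No use of the any OACs during the baseline period (the 180 days before the index date".

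Exclusions 2-5 (cardiac surgery, joint replacement, prosthetic valve procedure, venous thromboembolism) each look at baseline only; exclusion 5, for example, reads "Having a diagnosis of venous thromboembolism during the baseline period". Exclusion 1 (valvular, post-operative, rheumatic and mechanical-valvular AF) names baseline and the post-index period, but not the index date.

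In SAP 7.1.2.1 every diagnosis, score, drug and procedure term is taken in baseline, for example "stroke or SE diagnosis in baseline". Age is taken on the index date. Gender and age at NVAF diagnosis carry no window. Protocol 4.6, in the abstract, says instead that the study variables are collected at the index date.

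**The concern.** The day an anticoagulant is started is a natural day for its indication, and for diagnoses made at the same visit, to be recorded. The plan itself allows for this with AF. If the other records of that day are ignored, two things follow.

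- **Eligibility.** The exclusions can miss patients who started for another indication or straight after a procedure, although Protocol 9.1 describes the index date as initiation for the prevention of stroke/SE.
- **Adjustment.** A patient whose heart failure, diabetes or renal dysfunction is first coded on day 0 enters the propensity model as free of it. A stroke or bleed coded on day 0 is neither history nor outcome.

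The standardised differences in SAP 7.1.2.2 would not reveal the second problem, because they are computed on the same baseline variables. If those look balanced, the Cox model in SAP 7.1.2.5 contains treatment alone.

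**Working it through.** **Step 1: enumerate the days.** Baseline is days -180 to -1. Follow-up is day +1 onward. The days in neither set are {0}: exactly one, the index date. SAP 7.1.2.4 plots Kaplan-Meier time from the index date, but that sets the time origin; it does not move the start of follow-up in Protocol 9.1.

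**Step 2: could baseline be read as including day 0?** Two rules say no.

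- Under inclusion 3, if day 0 were in baseline, the index prescription itself would breach the washout and nobody would qualify.
- Inclusion 1 lists baseline, index date and post-index period as three separate windows.

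**Step 3: rule by rule.**

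| Rule | Window as written | Day 0 covered? |
|---|---|---|
| Inclusion 1 (AF) | baseline or index date | yes |
| Inclusion 3 (washout) | baseline | no, and rightly so |
| Exclusion 1 | baseline and post-index | not named |
| Exclusions 2-5 | baseline | no |
| Propensity diagnoses, scores, procedure | baseline (SAP 7.1.2.1); index date (Protocol 4.6) | conflicting |
| Propensity drugs | baseline (SAP 7.1.2.1); index date (Protocol 4.6) | conflicting |

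So a patient with AF and venous thromboembolism both first coded on the day warfarin starts satisfies inclusion 1 and is not caught by exclusion 5.

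**Step 4: an illustration of size.** No document gives the inputs; all are assumed. Take one binary confounder with prevalence p1 (apixaban) and p0 (warfarin), event-rate ratio R, a true treatment ratio of 1.00 and equal cohorts. A share m of carriers is coded only on day 0.

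- Share coded as carriers: w = (1 - m)(p1 + p0)/2
- Carriers hidden among the uncoded, in each arm: q = pm / [1 - p(1 - m)]
- Standardised rate in each arm: wR + (1 - w)[1 + (R - 1)q]

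For p1 = 0.20, p0 = 0.30, R = 2, m = 0.2:

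- w = 0.8 × 0.25 = 0.20
- q1 = 0.04/0.84 = 0.0476 and q0 = 0.06/0.76 = 0.0789
- rates are 0.40 + 0.80 × 1.0476 = 1.238 and 0.40 + 0.80 × 1.0789 = 1.263
- ratio = 1.238/1.263 = 0.980

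| Assumed p1 v p0, R | Unadjusted | m = 0.2 | m = 0.4 | m = 0.6 |
|---|---|---|---|---|
| 0.20 v 0.30, 2 | 0.923 | 0.980 | 0.963 | 0.948 |
| 0.15 v 0.30, 3 | 0.812 | 0.951 | 0.909 | 0.872 |

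With the prevalences exchanged the ratios invert: 0.948 becomes 1/0.948 = 1.055, and 0.872 becomes 1/0.872 = 1.147. The direction is as much an assumption as the size.

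**Step 5: set against the planning effects.** SAP 4.5 uses hazard ratios of 0.59 (major bleeding) and 0.53 (stroke/SE). Dividing out the mildest and the most extreme illustration gives 0.59/0.980 = 0.60 and 0.59/0.872 = 0.68, and 0.53/0.980 = 0.54 and 0.53/0.872 = 0.61.

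**Step 6: what widening exclusion 2 would catch.** In SAP 10.3.2 the cardiac-surgery list shares three codes with the Ablation list (150346710, 150262810, 150303310) and four with the Electrical defibrillation list (150275210, 150275310, 150336910, 150337010). Adding day 0 to exclusion 2 as coded would drop patients with any of these on the day their anticoagulant starts. Yet ablation and cardioversion are planned patient characteristics, and cardioversion is a propensity term.

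**The case against.** The literal gap is hard to dispute. The case against concerns how much follows from it.

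- **The covariate timing is contradictory rather than settled.** Protocol 4.6 points to the index date, and comorbidity rows in Protocol 9.5 and SAP 5.4 are redacted and could hold a look-back rule. This stands for the covariates: what can be shown is a conflict to reconcile. Protocol 4.6 does not touch the exclusions, and no visible text extends exclusions 2-5 to day 0.
- **Other rules overlap.** Exclusion 1, through codes recorded before or after day 0, and exclusion 7 (off-label or contraindicated use) may remove some same-day valve cases. This stands, so a reader should not infer that every same-day valve patient enters. Neither rule names venous thromboembolism or joint replacement.
- **A window ending on day -1 can be deliberate.** Claims dates do not give the order of events within a day, and a drug such as heparin given that day may be part of the treatment decision. This stands for the drug terms, so the point should not be stretched to them.
- **The bias is assumed.** A reader might infer that both primary hazard ratios remain confounded after weighting, in favour of apixaban. The documents do not support that: they give no day-0 share, no prevalences and no direction. Correlated terms in the model, such as antihypertensives and statins, would recover part of what is missed, and it is not shown that several conditions would compound.
- **E-values are planned (SAP 7.2.3).** They gauge how strong an unmeasured confounder would have to be. They do not correct a covariate taken over the wrong window or remove an ineligible patient.

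**Conclusion.** The gap is real on the operative text: one day, the index date, belongs to no window. Exclusions 2-5 miss records of that day, and under SAP 7.1.2.1 comorbidities first coded then count as absent. Confidence is high for the exclusions and lower for the covariates, because of Protocol 4.6 and the redacted rows. The number of patients affected, and the size and direction of any bias in either primary hazard ratio, cannot be computed from the documents. The range 0.98 to 0.87 shows only what one confounder could do under the assumptions in the working. Even its extreme end would not remove effects as large as those assumed in SAP 4.5. The point merits a change because the remedy is cheap and two analysts, one following Protocol 4.6 and one following SAP 7.1.2.1, would build different covariates.

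**What to change.** 1. Keep the anticoagulant washout (inclusion 3) at days -180 to -1, and follow-up from day +1.
2. For exclusions 3, 4 and 5, and for the diagnosis, score and procedure covariates in SAP 5.4 and 7.1.2.1, state the window as the 180 days before the index date or on the index date, as inclusion 1 already does for AF. Add the index date to exclusion 1 as well, keeping its post-index part.
3. Extend exclusion 2 in the same way only after the cardiac-surgery code list has been reconciled with the Ablation and Electrical defibrillation lists that share its codes.
4. Leave the drug covariates at days -180 to -1, and say so.
5. Align Protocol 4.6 with these windows.
6. Report a sensitivity analysis with the window as currently written.

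The cost is a wording change in Protocol 4.6, 9.1 and 9.3.2 and SAP 4.1.2, 5.4 and 7.1.2.1, the code-list reconciliation, and a re-run on structured data that need no new collection. There will be slightly fewer eligible patients. Because the order of events within the index day is unknown, a diagnosis made after the prescription that day would count as baseline; the sensitivity analysis shows how much this matters. If the programs already include day 0, only the text needs changing.

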9.2. Endpoints

- Primary effectiveness endpoint: stroke/SE (a composite of ischemic stroke, hemorrhagic stroke and SE)
- Primary safety endpoing: Major bleeding (any bleeding requiring hospitalization for treatment)

- Seconary effectiveness endpoint:
 - Cardiogenic embolic stroke
 - ➢ Ischemic stroke
- Secondary safety endpoint:
 - > Intracranial hemorrhage
 - Gastrointestinal bleeding
 - Intraocular bleeding

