7.1.2.3. Calculation of event rate

Patients who experience a clinical endpoint event after the earlier of their discontinuation of the index OAC, switching from the index OAC, withdrawal from the database, or the end of intended follow-up period will be censored. Patients who do not experience a clinical endpoint event will be censored at the earlier of their discontinuation of the index OAC, switching from the index OAC or withdrawal from the database will be censored.

Using the number of patients who experience each endpoints and the total observation period, incidence rate of each endpoint will be calculated and be presented as per 1,000 person-years.

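### Whether a stroke or bleed in the 45 days after run-out counts depends on whether the index anticoagulant is prescribed again afterwards

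*Protocol*

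**What the plan says.** Protocol 9.1 lists six ends of follow-up, and follow-up "ends depending on following outcomes which observed first". Rules 1-3 are the outcome under analysis. Below, day 0 or run-out is the calculated refill date (last refill plus days of supply), and the gap is the 45 days after it.

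- Rule 4 (discontinuation): no index OAC in the gap, "even though the patient has >1 medical encounter records after more than 45 days following the prescription refill date". End date: "The supposed prescription refill date is regarded as the last day of the follow-up for discontinued patients".
- Rule 5 (switch): a non-index OAC in the gap, with later encounters. End date: "The switched day is regarded as the last day of the follow-up for the switched patients".
- Rule 6 (withdrawal): no index OAC in the gap and "there is no data of the patient on the database after prescription refill date". End date: "The last medical encounter is regard as the last day of the follow-up for patients withdrawn from the database".

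Death is not among the six. SAP 7.1.2.3 adds the counting rule. "Patients who experience a clinical endpoint event after the earlier of their discontinuation of the index OAC", or of switching, withdrawal or the end of an intended follow-up period, are censored. Patients without an event are censored at the earliest of discontinuation, switching and withdrawal. The readable SAP does not restate or refine rules 4-6, and its data-derivation appendix (10.1) is marked not applicable. The one sensitivity analysis in SAP 7.2.3 is the E-value.

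**The concern.** Rule 4 cannot be applied until the gap has passed, yet it sets the end of follow-up to the start of the gap. Whether a gap event is inside follow-up is therefore settled by prescribing that comes after the event and may be a response to it. A bleed can be a reason not to prescribe the drug again. An admission can equally be the occasion on which it is prescribed. If the event changes the chance of a refill, censoring is informative for the outcome. The end date feeds the incidence rates, Kaplan-Meier curves, log-rank tests and Cox models for both primary endpoints, so an error here reaches all of them. The E-value addresses unmeasured confounding and would not detect it.

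**Working it through.** **The rules applied to one case.** A bleed occurs on gap day 20.

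| After the bleed | Rule met | End of follow-up | Bleed |
|---|---|---|---|
| Index OAC again on day 40 | 1 | day 20 | counted |
| No OAC again, later encounters | 4 | day 0 | dropped |
| Fatal, no further record | 4, if the encounter clause is a concession; otherwise neither 4 nor 6 | day 0, or undefined | dropped, or undefined |
| Non-index OAC on day 30, later encounters | 4 and 5 | day 0 or day 30; the SAP takes the earlier, day 0 | dropped |

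Rows 1 and 2 are the core of the point: the same event up to day 20, with opposite classification. Row 4 shows that rule 5's switch-day end date has no effect for a switch inside the gap.

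**Coverage of rules 4-6.** Without an index refill there are nine consistent combinations of non-index OAC in the gap, data in the gap, and number of encounters after day 45.

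| Reading of rule 4's encounter clause | No end date | One | Two |
|---|---|---|---|
| Condition, more than one encounter | 5 | 3 | 1 |
| Condition, at least one encounter | 2 | 5 | 2 |
| Concession | 0 | 6 | 3 |

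Under the concession reading, taking the earlier date as SAP 7.1.2.3 says resolves the three double cases.

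**The plan's own figures.** The documents give no refill data. SAP Table 2 supplies only the base rates, and its figures reproduce:

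- Major bleeding: 4(1.960 + 0.842)²/(ln 0.59)² gives 113 events; 113/[(0.025 + 0.0118)/2] = 6,141 patients.
- Stroke/SE: HR 0.53 gives 78 events; 78/[(0.0192 + 0.0098)/2] = 5,379 patients.

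The point does not affect them.

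**Size, on assumed inputs.** Let g be the share of counted time that lies in gaps. Let p1 and p0 be the chances that a gap is kept with and without an event, at the same gap day, and k = p1/p0. With true rate λ,

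counted events = λ(T_supply + k·T_gap), counted time = T_supply + T_gap, so rate factor = 1 − g(1 − k).

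| g | k = 0.5 | k = 1 | k = 1.5 |
|---|---|---|---|
| 0.02 | 0.990 | 1.000 | 1.010 |
| 0.08 | 0.960 | 1.000 | 1.040 |

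- Warfarin major bleeding, 25 per 1,000 person-years: 25 × 0.960 = 24.0 to 25 × 1.040 = 26.0.
- Warfarin stroke/SE, 19.2: 19.2 × 0.960 = 18.4 to 19.2 × 1.040 = 20.0.
- HR, g and k equal in both arms: unchanged.
- HR, g = 0.05, k = 0.5 in one arm and 1 in the other: 0.975/1.000 = 0.975, or 1/0.975 = 1.026.
- HR, g = 0.08, k = 0.5 against 1.5: 0.960/1.040 = 0.92, or 1.040/0.960 = 1.08.

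**Simulation check** (true rate 25; assumed 30-day supplies, a gap after 20% of them, 60% of event-free gaps refilled, so g = 8.2%; simulation standard error 0.04-0.07). Rule 4 gives 24.0, 25.0 and 26.1 for k = 0.5, 1 and 1.5. Run-out plus 45 days for everyone gives 25.0 at each k, and a zero-day allowance gives 24.9.

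**The case against.** *The first end observed governs, so a day-20 bleed precedes a discontinuation knowable only on day 46.* The lead sentence can be read that way. But rule 4's last sentence fixes the end date at run-out, and SAP 7.1.2.3 censors events after discontinuation. The specific text outweighs the general phrase.

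*The rules do yield a single date.* A reader might infer that rules 4-6 leave many patients with two end dates or none. The documents do not support that as a flat statement. SAP 7.1.2.3 takes the earlier date, which settles the in-gap switcher, and rule 4's encounter clause is worded as a concession, which closes the hole for patients last seen on gap days 1-45. What stands is narrower: rule 5 states an end date that never applies inside the gap, and the hole opens if a programmer treats the clause as a condition.

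*Rule 6.* A reader might also infer that ending withdrawn patients at the last encounter inflates rates, because an event creates its own encounter: major bleeding is "any bleeding requiring hospitalization for treatment". The mechanism exists, but its size cannot be derived. Patients with no later data may have left the hospital, and their later days could not produce a recorded event. No effect on the hazard ratio is shown.

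*Materiality.* This objection largely stands. Even the extreme factor of 1.083 would move the planning hazard ratios only from 0.59 to 0.64 and from 0.53 to 0.57, and equal behaviour in the arms leaves them unchanged.

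**Conclusion.** The look-ahead follows from the text: counting of gap events depends on later index prescribing, and gap events fatal before a new index prescription are never counted. The rate is understated if k < 1, overstated if k > 1 and unbiased if k = 1; the documents do not say which holds. The 4% limit on rates and the hazard-ratio factors hold only over the assumed ranges of g and k. It would go too far to say that the hazard ratios are biased, or biased towards apixaban: that needs a difference between arms in gap time or in post-event prescribing, and the documents report neither. The point should be corrected because censoring that depends on the outcome is avoidable here and nothing in the plan tests for it. Separately, rules 4 and 5 must be reconciled and the encounter clause clarified.

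**What to change.** In Protocol 9.1 and SAP 7.1.2.3, define one end-of-follow-up date that uses no later index refill. It is the earliest of:

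- the outcome under analysis;
- the first non-index OAC prescription;
- run-out plus one fixed allowance (for example the existing 45 days), with events and time inside it counted for everyone;
- a stated data cut-off.

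State the precedence when dates tie, and state that rule 4 does not require later encounters. Repeat both primary analyses with a zero-day allowance applied to every gap; that run uses nothing recorded after run-out.

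For patients with no record after run-out, state one end date that an event's own record cannot extend, for example run-out, and treat the rule 6 effect as a sensitivity check. Under that choice, an event that is the patient's only record after run-out is still left out, so report how many there are and what carrying these patients through the allowance would change. Counting the unobservable days of departed patients as event-free should not be the default.

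The cost is rewording two documents, reprogramming one date variable, one extra run of each primary analysis and the rule 6 check; no new data are needed. The downsides are that up to 45 off-supply days per stopper count as exposed in the main analysis, and that the zero-day run loses all follow-up after any late refill.

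### As printed, the switch rule does not end follow-up at a non-index OAC prescribed while index supply remains, so some time after that prescription is credited to the index cohort

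*Protocol*

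**What the plan says.** Protocol 9.1 (Observational period) lists the ways follow-up can end and takes whichever is observed first.

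- **Rule 4, discontinuation.** No further index OAC within 45 days of the prescription refill date, which is "calculated from the last refill date plus days of supply". This is the day the last index supply runs out. The rule adds "even though the patient has >1 medical encounter records after more than 45 days following the prescription refill date". The end date is run-out: "The supposed prescription refill date is regarded as the last day of the follow-up for discontinued patients".
- **Rule 5, switching.** A switch is recognised when a "non-index OAC is prescribed within 45 days after prescription refill date of the index OAC when the patient has 1> medical encounter records" beyond those 45 days. The end date is the switch: "The switched day is regarded as the last day of the follow-up for the switched patients".
- **Rule 6, withdrawal.** No further index OAC, and "there is no data of the patient on the database after prescription refill date". Then "The last medical encounter is regard as the last day of the follow-up for patients withdrawn from the database".

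SAP 7.1.2.3 says that patients without an endpoint event "will be censored at the earlier of their discontinuation of the index OAC, switching from the index OAC or withdrawal from the database". It does not define switching or say how it is dated, and SAP Appendix 1 (data derivation details) is marked as not applicable. The section between Protocol 9.3 and 9.5 and the one between SAP 4.3 and 4.5 are redacted, so this describes the readable text only.

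**The concern.** Rule 5 ties the switch to a window that opens at run-out. A change of anticoagulant made earlier, while index supply is still on hand, falls before the window, and no other rule ends follow-up on that day. Yet rule 5 itself treats the switch day as the natural end of index-drug follow-up, and the SAP lists switching as its own censoring event. Mid-supply switchers are therefore handled differently from the principle the plan states.

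These rules fix the person-time and the countable events for both primary endpoints, stroke/SE and major bleeding. A programmer who codes the printed window and one who codes the likely intention would produce different censoring dates for the same patient.

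**Working it through.** **1. Rules applied to timelines.** Put the last index fill on day 0, run-out on day R and the first non-index OAC on day s.

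- *s before R, no further index OAC, several encounters after R+45.* Rule 5 does not fire on day s. Rule 4 ends follow-up on day R, so the excess is R − s days. With R = 90 and s = 30 this is 60 days.
- *Same pattern, new drug refilled inside the window.* With R = 30, s = 15 and a new-drug refill on day 45, rule 5 can fire on day 45. The earlier date is still rule 4's day 30, an excess of 15 days. If rule 5 overrode rule 4 and used day 45, the excess would be 30 days.
- *No data after run-out.* With R = 30, s = 10 and last encounter on day 25, rule 6 ends follow-up on day 25, an excess of 15 days.

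For a switch day d = 1, …, S − 1 in a supply of S days, the excess under rule 4 is S − d. The maximum is S − 1 and the mean, if d is uniform, is S/2. Supply lengths are assumed:

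| Supply S (days) | Maximum excess | Mean excess |
|---|---|---|
| 30 | 29 | 15 |
| 60 | 59 | 30 |
| 90 | 89 | 45 |

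**2. The plan's own figures.** SAP Table 2 reproduces with Schoenfeld's formula (two-sided alpha 0.05, power 80%, 1:1): 4 × (1.960 + 0.842)² / (ln HR)² gives 113 events for HR 0.59 and 78 for HR 0.53. Patients are events divided by the mean annual rate: 113/0.0184 = 6,141 and 78/0.0145 = 5,379. The switch rule does not enter these figures. They serve below only as a scale.

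**3. Illustrative size.** Assumed, because the documents give none of it: 1% to 10% of each arm switches mid-supply (f), supply is 30 to 90 days, mean follow-up is 0.5 to 2 years, switching is between the two study drugs, and the post-switch hazard equals that of the other arm.

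Share of person-time affected: m = f × (S/2) / follow-up days.

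- Low: 0.01 × 15 / 730.5 = 0.0205%
- High: 0.10 × 45 / 182.6 = 2.464%

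Events affected, with equal m and equal person-time, are m × total: 0.02 to 2.8 of 113 major bleeds, and 0.02 to 1.9 of 78 stroke/SE events.

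Observed HR = [(1 − m) × HR + m] / [(1 − m) + m × HR]. At m = 2.464%:

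- Major bleeding: 0.6001/0.9899 = 0.606 (from 0.59)
- Stroke/SE: 0.5416/0.9884 = 0.548 (from 0.53)

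Shift in log HR divided by its standard error, 2/√events:

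- ln(0.6062/0.59) / (2/√113) = 0.0271/0.1881 = 0.14
- ln(0.5479/0.53) / (2/√78) = 0.0333/0.2265 = 0.15

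**4. Direction.** Let the post-switch hazard be k times that of the other drug (k = 1 to 3), and let each arm's share of switchers be 1% or 10%. Then HR = [(1 − mA) × HR + mA × k] / [(1 − mW) + mW × k × HR], where mA and mW are the apixaban and warfarin shares. The results run from 0.585 to 0.648 around 0.59, and from 0.528 to 0.590 around 0.53. The shift can go either way.

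**The case against.** The strongest reply is that the text is ambiguous rather than wrong. 'Within 45 days after' can be read as a deadline, which would capture a switch at any time up to 45 days past run-out. The surrounding text leans the same way: the earliest outcome governs, the switch day is the last day, and the SAP names switching separately. This makes a wording fault more likely than a chosen design. It does not remove the point, because the readable text nowhere states the deadline reading.

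A patient who stays on the new drug may also be prescribed it again inside the window, which meets rule 5, and 'the switched day' might then be taken as the day of the actual change. That is possible but not stated. If the day is the later refill, the excess does not shrink.

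It is also fair that claims do not show when a patient stopped taking the index drug. They show only that another OAC was prescribed.

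Finally, the size rests wholly on assumptions. The 2.5% figure is a corner case (10% switching mid-supply, 90-day supplies, half a year of follow-up), the non-index OAC need not be the comparator, and 113 and 78 are events needed for power, not events expected. All of that stands and limits the point to a minor one.

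**Conclusion.** The point holds as a minor defect. As printed, rule 5 does not censor a mid-supply switch on its own date, and where rule 4 applies up to the remaining days of supply are credited to the index cohort after another OAC was prescribed. The effect is probably small. With equal switching and equal hazards the most extreme assumed case moves HR 0.59 to about 0.606 and HR 0.53 to about 0.548, roughly 0.14 to 0.15 of a standard error at the planned event counts. None of this is a prediction.

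A reader might infer more, and the documents do not support it:

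- *That the primary hazard ratios are materially biased, or biased in a known direction.* No supply, switching or follow-up data are given, and the wider ranges need both unequal switching and a raised post-switch hazard.
- *That the credited time is time on a drug already stopped.* Only the new prescription is observed.
- *That rule 5's switch date never takes effect because the earlier date always wins.* Rule 5 can apply without rule 4. With run-out on day 30, another OAC on day 40 and the index OAC again on day 60, rule 4 fails because the index drug returns within 45 days.
- *That some patients have no end date at all.* A patient with no further OAC who is last seen 1 to 45 days after run-out falls outside rules 4 to 6 only if rule 4's encounter clause is a condition. Read as a concession, rule 4 covers that patient.

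**What to change.** This concerns analysis censoring only. In Protocol 9.1 and SAP 7.1.2.3:

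1. Define the switch date as the date of the first non-index OAC prescription after the index date, including while index supply remains. In the absence of an outcome event, end follow-up at the earliest of that date, the rule 4 discontinuation date and the rule 6 withdrawal date.
2. Reconcile `1>` in rule 5 with `>1` in rule 4. As printed, the first means fewer than one encounter.
3. For switches 1 to 45 days after run-out, where rules 4 and 5 can both apply, state one precedence, so that the protocol's first-observed principle, rule 5's switch day and the SAP's earlier-of wording give the same date.
4. Report by cohort how many patients end follow-up under each rule, so that the actual size becomes visible.

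The cost is wording in two documents and, if the program follows the printed window, a change to the censoring code and a rerun of the primary analyses. No new data are needed. If the code already censors at any non-index OAC, only the text needs aligning. Protocol 9.9 calls for an amendment if the change to the primary analyses is major, and Protocol 4.10 schedules analysis for July and August 2023. The downside is a small loss of person-time and events, including for patients who return to the index OAC after a single non-index prescription.
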